2.2. Study Design

This is a Phase 2b, randomized, double blind, placebo controlled, parallel group, multicenter study in participants with moderate to severe plaque psoriasis. After a screening period of - up to 6 weeks, eligible participants will be randomized in a 2:1:1:2:2 ratio such that participants will receive placebo or either one of four PF-06826647 daily dose levels (50 mg, 100 mg, 200 mg or 400 mg) every day during the Investigational Treatment Period for 16 weeks in a blinded fashion. All participants completing the 16 week Investigational Treatment Period will continue on to a 24 week non-placebo controlled Extension Treatment Period with double blind oral daily treatment, if per the Investigator judgment the participant is compliant with study procedures and continued participation presents no safety risks. The participants continuing into the Extension Treatment Period that were originally randomized to the 200 mg and 400 mg treatment groups will continue on their respective doses, while those randomized to one of the other treatment groups (including placebo) will be randomly assigned (at study baseline) to receive either 200 mg or 400 mg during the Extension Treatment Period. Participants who discontinue prior to Week 16 visit will enter the Follow-Up period and will not be eligible for the Extension Period.

Approximately 160 participants (40 participants in each of the following arms: placebo, 200 mg, and 400 mg; and 20 participants in each of the following arms: 50 mg and 100 mg) will be randomly assigned to a treatment group in order to ensure a minimum of 128 evaluable participants completing Week 16 (assuming a 20% dropout rate).

2.3. Schema

The total duration of study participation will be approximately 50 weeks, including up to 6 weeks Screening Period, 16 week Investigational Treatment Period, the 24 week Extension Treatment Period and a Follow-Up visit 4 weeks after the Extension Treatment Period.

Investigators, participants, and the sponsor study team (with the exception of the sponsor supply chain lead) will be blinded as to investigational drug.

If a participant is withdrawn from IP treatment, the participant will proceed with the Early Termination (ET) and Follow up visits per Schedule of Activities. If a participant uses prohibited medication, guidance in Section 10.8 of the protocol should be followed.

3. ENDPOINTS AND BASELINE VARIABLES: DEFINITIONS AND CONVENTIONS

3.1. Investigational Treatment Period

3.1.1. Primary Endpoint(s)

- Proportion of participants achieving PASI 90 (90% or greater improvement from Baseline) at Week 16.

3.1.2. Secondary Endpoint(s)

- Proportion of participants achieving PASI 75 (75% or greater improvement from Baseline) at time points specified in the Schedule of Activities (SoA) of the protocol.
- Proportion of participants with PGA score clear (0) or almost clear (1) and ≥ 2 points improvement from baseline at time points specified in the SoA.
- Proportion of participants with PGA score clear (0) or almost clear (1) at time points specified in the SoA.
- Proportion of participants achieving PASI 50 (50% or greater improvement from Baseline), PASI 100 (100% from Baseline) at time points specified in the SoA.
- Change from baseline and percent change from baseline in PASI scores at time points specified in the SoA.
- Change from baseline in Peak-Pruritus Numerical Rating Scale score at time points specified in the SoA.
- Proportion of participants with PSI overall score ≤ 8 with 0 or 1 for every individual domain time points specified in the SoA.
- Incidence and severity of adverse events, serious adverse events and withdrawals due to adverse events.
- Change from baseline in clinical laboratory values (chemistry, hematology & lipids).

- Incidence of clinically significant changes in ECG (heart rate, QT, QTc, PR and QRS intervals).

Note: For heart rate, the clinically significant abnormal criteria are < 40 or > 120 beats per minute (bpm).

- Change from baseline in vital signs (blood pressure, pulse rate and temperature measurements).
- Change from baseline Psoriasis Symptom Inventory at time points specified in the SoA.

CCI [Redacted]

- [Redacted]
- [Redacted]
- [Redacted]
- [Redacted]
- [Redacted]
- [Redacted]
- [Redacted]
- [Redacted]
- [Redacted]
- [Redacted]
- [Redacted]
- [Redacted]
- [Redacted]

CCI [Redacted]

CCI [Redacted]

CCI [Redacted]

3.2. Extention Treatment Period

3.2.1. Primary Endpoint(s)

- Incidence and severity of adverse events, serious adverse events and withdrawals due to adverse events.
- Change from baseline in clinical laboratory values (chemistry, hematology & lipids).
- Incidence of clinically significant changes in ECG (heart rate, QT, QTc, PR and QRS intervals).
- Change from baseline in vital signs (blood pressure, pulse rate and temperature measurements).

CCI

[REDACTED]

[REDACTED]

[REDACTED]

[REDACTED]

[REDACTED]

[REDACTED]

[REDACTED]

[REDACTED]

[REDACTED]

[REDACTED]

[REDACTED]

3.3. Baseline Variables

Baseline will be defined as the last available measurement prior to randomization on Day 1, if a Day 1 measurement is not available, the value from the Screening visit can be used. For the PRO endpoints baseline will be defined as the average of all values/values recorded on Day 1 or the last available screening visits when missing Day 1 measurement.

CCI

3.4. Safety Endpoints

Safety will be assessed by the spontaneous reporting of AEs, physical examinations, and clinical laboratory results in all subjects who receive at least one dose of the investigational product. Unscheduled safety assessments may be performed at any time during the study to assess any perceived safety concerns. Endpoints will be assessed as:

- Incidence of treatment emergent adverse events.
- Incidence of SAEs and AEs leading to discontinuation.
- Incidence of clinical abnormalities and change from baseline in selected clinical laboratory values, ECG measurements, and vital signs.

The safety endpoints will be defined in accordance with Clinical Data Interchange Standards Consortium (CDISC) and Pfizer Standards (CaPS).

3.4.1. Adverse Events

An adverse event will be considered a Treatment-Emergent Adverse Event (TEAE) if the event started during the effective duration of treatment. All events that start on or after the first dosing day (after the first application of IP) and time/start time, if collected, but before the last dose plus the lag time will be flagged as TEAEs. The algorithm will not consider any events that started prior to the first dose date.

A 3-tier approach will be used to summarize AEs. Under this approach, AEs are classified into 1 of 3 tiers. Different analyses will be performed for different tiers (see [Section 6.8.1](#)).

Tier 1 events: These are prespecified events of clinical importance and are maintained in a list in the product's Safety Review Plan.

Tier 2 events: These are events that are not tier 1 but are "common." A Medical Dictionary for Regulatory Activities (MedDRA) preferred term (PT) is defined as a Tier 2 event if there are at least 4 in any treatment group.

Tier 3 events: These are events that are neither Tier 1 nor Tier 2 events.

3.4.2. Laboratory Data

Below is a list of hematology and serum chemistry test parameters.

- Hematology: hemoglobin, hematocrit, red blood cell count, reticulocyte count, platelet count, white blood cell count with differential, total neutrophils, eosinophils, monocytes, basophils, lymphocytes, coagulation panel.
- Serum chemistry: blood urea nitrogen, creatinine, creatine phosphokinase, glucose, sodium, potassium, chloride, calcium, total bicarbonate, aspartate aminotransferase, alanine aminotransferase, gamma-glutamyl transferase, bilirubin, alkaline phosphatase, uric acid, albumin, total protein, total cholesterol, low-density lipoprotein (LDL), high-density lipoprotein (HDL), triglycerides.

3.4.3. Vital Signs, including Height and Weight

Vital sign measurements are body temperature, pulse rate, and blood pressures.

Weight is collected at pre- and post-treatment.

3.4.4. Physical Examinations

Complete physical examinations consist of assessments of the general appearance, skin, head, eyes, ears, nose, throat, cardiovascular, respiratory (lung), gastrointestinal, and neurological systems.

4. ANALYSIS SETS (POPULATIONS FOR ANALYSIS)

4.1. Full Analysis Set (FAS)

As specified in the protocol, the analysis of the efficacy, patient reported outcome **CCI** [REDACTED] endpoints will be performed for the modified intent-to-treat (mITT) population, defined as all randomized subjects who receive at least 1 dose of investigational product (PF-06826647 or placebo). This population is also called the Full Analysis Set (FAS).

4.2. Safety Analysis Set

The safety analysis set (SAS) will be all subjects who receive at least 1 dose of investigational product. The final safety database will include all reported safety data at the time of database release.

CCI [REDACTED]
[REDACTED]

4.4. Treatment Misallocations and Missing Data

If a subject was:

- Randomized but not treated: the subject will appear on the subject evaluation table as randomized but not treated; this is the extent of how much the subject will be reported;
- Treated but not randomized: the subject will be reported under the treatment they actually received for all safety analyses, but will not be included in the efficacy analyses;
- Randomized but took incorrect treatment: If a subject received the incorrect treatment for the whole duration of the study, then the subject will not be reported for any efficacy analysis, but will be summarized under the treatment they actually received for all safety analyses; if a subject received the incorrect treatment at only some dosing occasions then the subject will be reported under their randomized treatment group for both efficacy and safety analyses. If sufficient doses were incorrect and therefore deemed a major protocol deviation, the subjects may be excluded as sensitivity analysis.

CCI [REDACTED]

For the continuous PRO variables such as pruritus NRS, CCI [REDACTED] rules suggested by the developers of these instruments will be followed in calculating the missing values. If these rules are not enough for imputing a value, then the missing values will be handled in the same way as non-PRO variables.

Data for all participants will be assessed to determine if participants meet the criteria for inclusion in each analysis population prior to unblinding and releasing the database and classifications will be documented per standard operating procedures.

Population	Description
Full analysis set	All participants randomly assigned to IP and who apply at least 1 dose of IP.
CCI [REDACTED]	[REDACTED]
Safety	All participants who receive at least 1 dose of study intervention. Participants will be analyzed according to the intervention they actually received. A randomized but not treated participant will be excluded from the safety analyses.

The following patient level data descriptions are also required for defining the pre-specified analyses:

Defined Analysis Data set (at the data level) – endpoint specific	Description
Primary Estimand Categorical Endpoint Set	This set will include all patients in the mITT population. All data for a subject after the initiation of prohibited medications, withdrawal of either study drug or the study itself will be set to a failure. Any additional missing data will be recorded as a failure. Subjects will have either a success or failure in the dataset for all scheduled visits.
Secondary Estimand Continuous Endpoint Set	This set will include all patients in the mITT population. All data for a subject after the initiation of prohibited medications will be set to missing. Note the secondary estimand requires multiple imputation which will be performed on this dataset, the multiple imputations themselves will not be saved in the database.
Observed Efficacy Set	This set will include all patients in the mITT population and all observed data and includes all data recorded from the CRF pages. No data will be set to missing or modified from the original CRF record.

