9.3. Populations for Analysis

For purposes of analysis, the following populations are defined:

Population	Description
Safety Analysis Set	All participants randomly assigned to IP and who take at least 1 dose of IP. Participants will be analyzed according to the product they actually received.

Defined Population for Analysis	Description
Modified Intention to Treat (mITT)	All participants randomly assigned to IP and who take at least 1 dose of IP.
CCI	

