9.4.1. Efficacy Analyses

Endpoint	Statistical Analysis Methods
Primary and key secondary: PASI 90 and PASI 75 at Week 16	A landmark analysis of the composite endpoint; achieving a PASI 90 response (a score of 90% improvement from Baseline) without prohibited medication, while remaining on study and providing data. The analysis will use the mITT analysis set. Based on the definition of the composite endpoint all participants in the mITT set will have a response for all visits (ie, there is no missing data). The proportions responding and the risk difference between treated arms and their corresponding placebo arm will be analyzed using an unconditional exact method: risk differences and corresponding 2-sided unconditional exact 90% confidence intervals will be computed using the Chan and Zhang (1999) method. Multiplicity adjustment will be utilized; details of multiplicity adjustment will be provided in the SAP.

Other continuous secondary endpoints at time points specified in the [Schedule of Activities](#) including; absolute PASI, change from baseline PASI, percent change from baseline PASI, absolute and change from baseline Itch Severity Score, absolute and change from baseline Psoriasis Symptom Inventory will be analyzed as described for the E2 estimand along with descriptive statistics and possibly graphical displays. No adjustments for multiplicity will be made for these endpoints.

Other binary secondary endpoints at time points specified in the [Schedule of Activities](#) including, PASI 50, PASI 100, PGA of clear or almost clear and proportions of participants achieving a Psoriasis Symptom Inventory Score of 0 or 1 will be analyzed as described for the primary estimand along with descriptive statistics and possibly graphical displays. No adjustments for multiplicity will be made for these endpoints.

CCI [REDACTED]

All endpoints in Extension Treatment Period will be analyzed with descriptive statistics and graphical displays when appropriate. Details of the analyses of the Investigational Treatment Period and Extension Treatment Period will be included in the Statistical Analysis Plan (SAP).

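### SAP 4.4 drops participants who received the wrong treatment throughout from every efficacy analysis, although the mITT/FAS definitions include them

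*SAP*

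**What the plan says.** The rule is in SAP 4.4, in the bullet on participants who were randomised but took incorrect treatment. Its trigger is "If a subject received the incorrect treatment for the whole duration of the study" and its consequence is "then the subject will not be reported for any efficacy analysis". The participant still counts in the safety analyses, under the treatment actually received.

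The same bullet handles partial errors differently. A participant given the wrong treatment on only some occasions stays in the randomised group for efficacy. If the errors amount to a major deviation, exclusion is allowed only as a sensitivity analysis.

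The efficacy population is defined in three places, none with a misallocation exception:

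- SAP 4.1, for the mITT population, also called the FAS: "defined as all randomized subjects who receive at least 1 dose of investigational product". The SAP adds that the product may be PF-06826647 or placebo.
- SAP 4.4, FAS row of the population table: "All participants randomly assigned to IP and who apply at least 1 dose of IP".
- Protocol 9.3, for the mITT: "All participants randomly assigned to IP and who take at least 1 dose of IP".

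Of the data set used for the primary analysis, SAP 4.4 says: "This set will include all patients in the mITT population".

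**The concern.** A participant who was randomised, dosed and given the wrong study treatment throughout belongs to the primary analysis set under three definitions and is removed from it by one bullet. Two programmers working from the same SAP could build different denominators for the PASI 90 comparison.

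The removal depends on something that happens after randomisation, so the arms compared would no longer be exactly the arms that were randomised. If a case arose, the sponsor would have to choose between the two readings at that point, and a choice made then is harder to defend than one fixed in advance.

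**Working it through.** No planned figure in the documents depends on this rule, so there is none to reproduce. The check is mainly a comparison of texts, followed by an illustration of size.

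**Does the participant meet the definition?** The definitions set two conditions: randomised, and at least one dose of investigational product. SAP 4.1 counts either drug or placebo as investigational product. A participant randomised to placebo who took active tablets throughout, or the reverse, meets both conditions.

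**Does the primary data set keep the participant?** Yes. SAP 4.4 puts every mITT patient in the Primary Estimand Categorical Endpoint Set, with a success or failure at each scheduled visit. Protocol 9.4.1 likewise gives every mITT participant a response at every visit.

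**Does anything reconcile this with the exclusion?** Nothing in the available text does. SAP 4.1 presents its definition as the protocol's own, and the protocol text supplied has no misallocation exception.

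**Is the trigger defined at the primary analysis?** Not clearly. SAP 5 places that analysis at the point when all participants have completed 16 weeks or withdrawn, but treatment can run to Week 40. The rule does not say whether the whole study means 16 weeks, 40 weeks or the participant's own time on treatment. On the last reading, someone given the wrong treatment who stops early would be deleted by the misallocation bullet, whereas the endpoint-set definition would count that person as a failure.

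**Size of the exclusion (illustration).** The documents give no misallocation rate, so one or two removals per arm is an assumption. Inputs: 40 or 20 participants per arm (Protocol 4.1), and an active response of 5% + 35% = 40% (Protocol 9.2). With r responders among n, removing one responder gives (r − 1)/(n − 1) and removing one non-responder gives r/(n − 1).

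| Arm | Full | One responder removed | One non-responder removed |
|---|---|---|---|
| n = 40, r = 16 | 40.0% | 15/39 = 38.5% (−1.5) | 16/39 = 41.0% (+1.0) |
| n = 20, r = 8 | 40.0% | 7/19 = 36.8% (−3.2) | 8/19 = 42.1% (+2.1) |

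With two removed, both responders or both non-responders, the ranges are 14/38 = 36.8% to 16/38 = 42.1% (n = 40) and 6/18 = 33.3% to 8/18 = 44.4% (n = 20).

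The 40% is the sample-size planning value. Protocol 4.3 projects only 3% and 13% for the two 20-participant arms (50 mg and 100 mg).

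**Size of the dilution if the participant is kept (illustration).** Inputs: placebo response 5% (Protocol 9.2) and projected response at 400 mg 83% (Protocol 4.3). With one of 40 placebo-assigned participants taking 400 mg throughout, the expected placebo rate is (39 × 0.05 + 0.83)/40 = 2.78/40 = 6.95%, a rise of about 2 points.

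**The case against.** The best defence is that the case is very unlikely. Allocation runs through IRT. For someone completing Week 16, the treatment would have to be wrong at every dispensing visit from Baseline to Week 12, and any lesser error leaves the participant in the randomised group. A specific rule can also be read as qualifying a general definition, and no mITT definition says in words that analysis is by randomised arm. If misallocation is unrelated to prognosis, the exclusion costs precision and has no expected direction, whereas keeping the participant pulls the contrast towards zero.

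Much of this stands. Rarity limits the impact, and no bias in a given direction has been shown. The as-randomised principle is inferred, from the partial-misallocation rule and from the reservation of treatment actually received for safety. None of this removes the contradiction over who is in the primary set.

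A reader might infer more than the documents support:

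- **That the rule breaches the primary estimand, which applies regardless of compliance.** Protocol 6.4 defines non-compliance as taking under 80% or over 120% of dosing as directed. Someone supplied the wrong kit can be fully compliant, so misallocation is not the intercurrent event that E1 names.
- **That such cases cannot be identified before unblinding.** Protocol 6.2.1 and 6.3.1 describe unique container numbers and an IRT confirmation report, and SAP 2.3 leaves the supply chain lead unblinded. The requirement to classify before unblinding is not shown to be unworkable.
- **That a kit-labelling fault could affect several participants in one arm.** Nothing in the documents points to one.
- **That one exclusion typically moves an arm by 2.5 or 5 points.** These are the ceilings, 1/40 and 1/20, reached only when an arm loses its sole responder or sole non-responder.

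**Conclusion.** The point holds as a conflict between a stated exclusion and the defined primary analysis set. SAP 4.4 removes randomised, dosed participants whom SAP 4.1, its own FAS row and Protocol 9.3 include, and it does so on a post-randomisation event. It also departs from the approach its own bullet takes to partial errors, and its trigger is not anchored to the 16-week primary period.

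The practical size is small and conditional: nothing if no whole-study misallocation occurs, otherwise about 1.0 to 1.5 points per participant in a 40-participant arm or 2.1 to 3.2 points in a 20-participant arm. This assumes a 40% response and one removal, and it describes movement in the observed rate, not a demonstrated bias. The correction is worth making because the primary denominator should not depend on which paragraph is followed.

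**What to change.** In SAP 4.4, replace the whole-study exclusion with a rule that these participants remain in the FAS, are analysed under their randomised treatment for efficacy and under the treatment received for safety, and are excluded only in a sensitivity analysis. This extends to whole-study errors the efficacy handling that the bullet already gives to partial ones. It also means the primary analysis no longer depends on what counts as the whole study. If the sensitivity analysis keeps that trigger, state the period it refers to.

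If the sponsor prefers exclusion, the mITT/FAS definition should be changed in both documents. Protocol 9 requires a protocol amendment if that counts as a major modification of the primary analysis.

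The cost is one SAP sentence, no change to the planned 160 participants, and some dilution if a case occurs. In the placebo example above, the expected placebo rate would rise by about 2 points. That figure rests on the projected 83%, which Protocol 4.3 itself describes as an uncertain extrapolation from Week 4. The sensitivity analysis would show how much any such case matters.

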4.5. Handling of Missing Data due to COVID-19 Pandemic

Due to the COVID-19 pandemic, as part of control measures some of the important endpoint data, such as PASI and PGA scores, are being collected via remote visit. If data are available for those visits, then those will be incorporated in the analysis; any incomplete data or missing data collected via remote visit will be removed from the primary analysis. Hence no non-responder imputation will be done on missing binary data collected via remote visit.

All participants that are discontinued due to COVID-19 will be removed from the primary and secondary efficacy endpoint analyses.

All missing data due to COVID-19 pandemic will be used 'as is' for the sensitivity analysis and the safety analysis.

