2.1.1. Primary Estimand(s)

The primary estimand will provide a population level estimate of the treatment effect of PF-06826647 on the proportion of participants with moderate to severe plaque psoriasis achieving PASI 90 (90% or greater improvement from Baseline) under the hypothetical scenario that prohibited medications are not used regardless of dosing compliance.

- Population: *Participants with moderate to severe plaque psoriasis as defined by the inclusion and exclusion criteria without the benefit of additional prohibited medication regardless of compliance.*
- Variable: *Proportion of participants achieving PASI 90 (90% or greater improvement from Baseline) at Week 16.*
- Intercurrent events: *A) Prohibited medication –response will be considered negative for participants after receiving prohibited medication. B) Withdrawal and all other events leading to missing data will be treated as in A). C) Inadequate compliance – participants data will be used as recorded.*

CCI

- Population-level summary: *The difference in proportions between treated and placebo response rates.*

The primary estimand strategy will be applied to the following secondary endpoints:

- Proportion of participants with PGA score clear (0) or almost clear (1) and ≥ 2 points improvement (daily and weekly) at time points specified in the SoA.
- Proportion of participants with PGA score clear (0) or almost clear (1) at time points specified in the SoA.
- Proportion of participants with PSI overall score ≤ 8 with 0 or 1 for every individual domain time points specified in the SoA.
- The primary estimand will also be used for PASI 75 response at all time points specified in the Schedule of Activities.

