2.1.2. Secondary Estimand(s)

The secondary estimand will provide a population level estimate of the treatment effect of PF-06826647 on continuous endpoints, especially the change from baseline and the percent change from baseline in PASI scores under the hypothetical scenario that prohibited medication is not used regardless of dosing compliance.

- Population: *Participants with moderate to severe plaque psoriasis as defined by the inclusion and exclusion without the benefit of additional prohibited medications regardless of compliance.*
- Variable: Change from baseline or the percentage change from baseline in PASI at Week 16.
- Intercurrent Events: *A) Prohibited medication – all scores after participants receive prohibited medication will be omitted from the analysis and treated as missing scores. Missing scores will be imputed based on the assumption that participants do not benefit from the IP treatment. B) Withdrawal and all other events leading to missing data will be treated similarly as in A). C) Inadequate compliance – participants data will be used as recorded.*
- Population-level summary: The mean difference between treated and placebo arms of the change from baseline/percentage change from baseline PASI score.

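### SAP 4.5 drops COVID-19 losses from the primary analysis without a Week 16 limit, so the result would not be estimand E1 and no visible analysis would count those losses as non-response in the full mITT set

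*SAP*

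**What the plan says.** SAP 4.5 sets three rules for pandemic losses.

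- Discontinuations: "All participants that are discontinued due to COVID-19 will be removed from the primary and secondary efficacy endpoint analyses".
- Remote visits: "any incomplete data or missing data collected via remote visit will be removed from the primary analysis", followed by "Hence no non-responder imputation will be done on missing binary data collected via remote visit".
- Sensitivity and safety analyses: "All missing data due to COVID-19 pandemic will be used 'as is' for the sensitivity analysis and the safety analysis".

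The rest of the plan treats the same losses differently. Under E1 (SAP 2.1.1), prohibited medication makes the response negative, and "Withdrawal and all other events leading to missing data will be treated as in A". For the Primary Estimand Categorical Endpoint Set, which covers the whole mITT population, SAP 4.4 adds: "Any additional missing data will be recorded as a failure". It continues: "Subjects will have either a success or failure in the dataset for all scheduled visits". SAP 5.3 and 6.1.1.1 say that this set has no missing values, Appendix 1 gives the failure rule for the full analysis set, and Protocol 9.4.1 says that every mITT participant has a response at every visit. For the continuous estimand E2 (SAP 2.1.2), "Withdrawal and all other events leading to missing data will be treated similarly as in A", which there means imputation. Protocol 9.1.1 describes control-based multiple imputation for the primary estimand.

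**The concern.** Someone who leaves before Week 16 because of COVID-19 is a non-responder under E1, absent under SAP 4.5, and multiply imputed under Protocol 9.1.1. In the visible text, the E1 sections carry no COVID-19 exception and no reference to 4.5. If 4.5 is followed, the reported difference belongs to a smaller population than the one E1 names, and nothing labels it as a different quantity. Nor is there a fallback: the only sensitivity analysis of PASI 90 (SAP 6.1.1.2) uses observed data.

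Section 4.5 also sets no time limit. Participants who complete Week 16 go on to a 24-week extension (SAP 2.2), and the primary analysis waits until everyone has finished Week 16 or withdrawn (SAP 5). Early enrollees can therefore be in the extension when it is run. Taken literally, the rule would delete a recorded Week 16 response because of something that happened afterwards.

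**Working it through.** **1. Arm sizes.** Protocol 9.2 assumes 32 completers per arm for placebo, 200 mg and 400 mg, 16 each for 50 mg and 100 mg, and 20% dropout. 128/(1 − 0.20) = 160, 32/0.8 = 40 and 16/0.8 = 20, so the plan's figures reproduce. They fix the denominators below but say nothing about which missing-data rule applies.

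**2. The rules side by side for the Week 16 primary analysis.**

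| Case | SAP 2.1.1, 4.4, 5.3, 6.1.1.1, App. 1; Protocol 9.4.1 | SAP 4.5 | Protocol 9.1.1 |
|---|---|---|---|
| COVID-19 discontinuation before Week 16 | failure | participant removed | control-based imputation |
| Week 16 remote visit, PASI missing | failure | removed, no imputation | control-based imputation |
| Week 16 visit missed because of COVID-19, no remote visit, no discontinuation | failure | not addressed for the primary analysis | control-based imputation |
| Valid Week 16 PASI, later COVID-19 discontinuation in the extension | as observed | removed, if read literally | as observed |

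**3. Effect on the difference, losses before Week 16.** COVID-19 counts are assumed. Participants with data respond at the planned 40% versus 5% (Protocol 9.2: 5% placebo plus 35 points). With missing fractions m1 (active) and m0 (placebo):

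E1 difference = 0.40(1 − m1) − 0.05(1 − m0); removal difference = 0.40 − 0.05 = 0.35.

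| Missing | E1 | SAP 4.5 | 4.5 minus E1, points |
|---|---|---|---|
| 5% in both arms | 0.3325 | 0.35 | +1.75 |
| 10% in both arms | 0.315 | 0.35 | +3.5 |
| 20% in both arms | 0.28 | 0.35 | +7 |
| 20% active only | 0.27 | 0.35 | +8 |
| 20% placebo only | 0.36 | 0.35 | −1 |

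**4. Effect on the test.** The p-values are one-sided, unconditional exact (score statistic, maximised over the common rate) and unadjusted. Counts are placebo versus active. Those removed are counted as failures under E1.

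At about the planned effect:
- E1, 2/40 vs 14/40: p = 0.0005.
- Eight removed from each arm, 2/32 vs 14/32: p = 0.0003.
- Eight removed from placebo only, 2/32 vs 14/40: p = 0.0024.

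All are below 0.05/4 = 0.0125, the strictest level for four active arms.

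Near the threshold:
- E1, 2/40 vs 8/40: p = 0.024.
- Four removed from active only, 2/40 vs 8/36: p = 0.016.
- Four removed from placebo only, 2/36 vs 8/40: p = 0.037; eight, 2/32 vs 8/40: p = 0.057.
- Four removed from each arm, 2/36 vs 8/36: p = 0.022.
- A 20-person arm, 2/40 vs 4/20: p = 0.064; with 10% removed from both arms, 2/36 vs 4/18: p = 0.063; with 20%, 2/32 vs 4/16: p = 0.046.

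**5. Literal reading, removals after Week 16.** These participants have observed Week 16 responses.
- Start from 2/40 vs 8/40 (15.0 points, p = 0.024). Two active responders removed, 2/40 vs 6/38: 15.8% − 5.0% = 10.8 points, p = 0.069.
- Same start, one placebo responder removed, 1/39 vs 8/40: 20.0% − 2.6% = 17.4 points, p = 0.008.
- At the planned rates, 2/40 vs 16/40 (35 points), four active responders removed, 2/40 vs 12/36: 33.3% − 5.0% = 28.3 points, p = 0.001.

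**The case against.** The best defence is that 4.5 is a dedicated section, added in SAP version 2.0, which names non-responder imputation and switches it off. A specific, later rule normally overrides a general one, and SAP 4.4 has population membership settled and documented before unblinding. This largely stands. A reader might infer that the primary denominator is simply undetermined for losses before Week 16; the documents do not support that, because 4.5 is the more natural rule to follow. But an override does not reconcile the plan. It makes the statements about full mITT inclusion and no missing values untrue and changes the estimand without saying so. Classification before unblinding limits post-hoc choice but does not settle the estimand.

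A reader might also infer that the sponsor means to discard valid Week 16 results. The documents do not show this. Section 4.5 is headed as missing-data handling, keeps remote-visit data that are available, and the primary endpoint is at Week 16. The gap is in the wording.

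Third, a reader might infer that removal favours the drug. The documents give no COVID-19 counts, and the direction depends on which arm loses participants and whether they were responders. The near-threshold examples were chosen to show sensitivity, and decisions use Hochberg-adjusted testing (SAP 5.1), so crossing an unadjusted 0.05 is not itself a trial decision. The 20% case equals the plan's whole dropout allowance.

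Lastly, several sections contain redactions. SAP 6.1.1.1 and Appendix 1, read alone, do describe the full-mITT non-responder analysis. It disappears only once 4.5 is applied, and only the visible text can be checked.

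**Conclusion.** The point holds and should be fixed. If 4.5 governs, as is most plausible, the primary estimate is not E1, the statements in SAP 4.4, 5.3 and 6.1.1.1 and Protocol 9.4.1 are wrong as written, and no visible analysis gives the full-mITT non-responder result. Removing discontinued participants conflicts with E2 in the same way. The missing Week 16 limit is a separate defect of wording.

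The actual size and direction are unknown. Under the assumed losses and planned rates, the two rules differ by 1.75 to 7 points when both arms lose equally, and by +8 to −1 when only one arm loses 20%. Removals from 14/40 versus 2/40 leave significance unchanged; a result near the threshold can move either way. Confidence is high on the textual conflict and the missing time limit. Whether pandemic losses count as non-response or are excluded is partly a design choice, so the defect is that the choice is undeclared and unaligned.

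**What to change.** State one rule. There are two acceptable routes.

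1. Keep E1: retain all mITT participants, count COVID-19 losses before Week 16 and missing Week 16 remote-visit data as non-response, and make the 4.5 removal a named sensitivity analysis.
2. Keep removal as primary: declare it as a different estimand through a protocol amendment, which Protocol 9 and SAP 2 require for a major change to the primary analysis, and name the full-mITT non-responder analysis as a sensitivity analysis.

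Under either route:
- Limit the COVID-19 rule to data missing at or before Week 16, so that a valid Week 16 PASI always counts.
- Say how a visit missed because of COVID-19 is handled when there was neither a remote visit nor a discontinuation.
- Make the matching choice for E2.
- Align SAP 2.1.1, 2.1.2, 4.4, 4.5, 5.3, 6.1.1.1, 6.2.1.1, 6.2.2.1, 6.2.5.1 and Appendix 1 with Protocol 9.1.1 and 9.4.1.
- Tabulate COVID-19 discontinuations and missing remote visits by arm and by timing (before or after Week 16).

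The cost is SAP wording, alignment of the protocol text (a formal amendment under route 2), one extra analysis and one table. No new data are needed. The drawback of route 1 is that pandemic logistics count as treatment failure, which lowers response rates if such losses are common.
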